10.3.2.4. Adverse Events of Special Interest

The following specific treatment-emergent adverse events of special interest, which may be searched using Standardized MedDRA queries, will be summarized:

- Hepatotoxicity, identified via the following SMQs:
 - Hepatic failure, fibrosis and cirrhosis and other liver damage-related conditions (SMQ)
 - Hepatic disorders (SMQ)
- Thrombocytopenia, identified via the following SMQs/HLT:
 - Hematopoietic thrombocytopenia (SMQ)
 - Haemorrhages (SMQ)
 - All TEAEs which code into the "Platelet disorders NEC" HLT
- Cardiac events, identified via the following SMQs:
 - Ischemic heart disease (SMQ)
 - Cardiomyopathy (SMQ)
 - Cardiac arrhythmias (SMQ)
 - Embolic and thrombotic events (SMQ)
 - Myocardial infarction (SMQ)
- Ganglionitis, with potential cases identified by reviewing all TEAEs which code to the "Nervous System Disorders" SOC

For each AE of interest category, the number and percentage of patients experiencing at least one TEAE in the search for the event of interest will be presented overall. AEs of special interest will be summarized by SOC and PT overall.

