12.1.2. Physical Examinations

Physical examinations will be conducted by the Investigator or designee as specified in the SoA ([Appendix 1](#)). The Day 1 physical examination will be performed prior to the start of gene replacement therapy infusion. Physical examinations include a review of the following systems:

head, eyes, ears, nose and throat (HEENT), lungs/thorax, cardiovascular, abdomen, musculoskeletal, dermatologic, lymphatic, neurologic, and genitourinary. Specifically, the neurological exam should include detailed, age-appropriate sensory testing (such as examination of proprioceptive, vibratory, tactile and pain sensation) at each visit. Any clinically significant abnormal finding should be recorded as an adverse event. Further clinical evaluation should be considered per judgment of the investigator.

The head circumference shall be measured with each physical examination. To measure head circumference, the examiner should securely wrap a flexible measuring tape around the circumference of the head, above the eyebrows over the broadest part of the forehead, above the ears, and over the most prominent part of the occiput. The measurement should be taken 3 times, and the largest measurement should be recorded to an accuracy of 0.1 centimeters.

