13. ADVERSE AND SERIOUS ADVERSE EVENTS

13.1. Definition of Adverse Events

13.1.1. Adverse Event

An AE is the development of an undesirable medical condition or the deterioration of a pre-existing medical condition following or during exposure to a pharmaceutical product, whether or not considered casually related to the product. In clinical studies, an AE can include an undesirable medical condition occurring at any time, including baseline or washout periods, even if no trial treatment has been administered.

All AEs (related or not related) that occur after signing of the informed consent through the last trial visit will be collected and recorded in the eCRF.

All AEs will be classified in accordance with the CTCAE version 4.03 outlined in [Table 4](#).

Table 4: Common Terminology Criteria for Adverse Events

Grade	Definition
1	Mild; asymptomatic or mild symptoms; clinical or diagnostic observations only; intervention not indicated
2	Moderate; minimal, local or noninvasive intervention indicated; limiting age-appropriate instrumental ADL. ^a
3	Severe or medically significant, but not immediately life-threatening; hospitalization or prolongation of hospitalization indicated; disabling; limiting self-care ADL. ^b
4	Life-threatening consequences; urgent intervention indicated.
5	Death related to AE.

Source: Common Terminology Criteria for Adverse Events (version 4.03) [40]

^a Instrumental ADL refer to preparing meals, shopping for groceries or clothes, using the telephone, managing money, etc.

^b Self-care ADL refer to bathing, dressing and undressing, feeding self, using the toilet, taking medications, and not bedridden.

Additionally, a DSMB/DMC will review safety data on a quarterly basis. A detailed description of the DSMB/DMC, its role in this trial, and the timing and process of the scheduled reviews will be described in a DSMB/DMC Charter.

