13.1.3. Adverse Events of Special Interest

The following are considered AEs of special interest (AESIs):

- Hepatotoxicity
- Thrombocytopenia
- Cardiac adverse events
- Sensory abnormalities suggestive of ganglionopathy

All AESIs (related and not related) that occur after signing of the informed consent through 30 days after the last study visit, irrespective of grade, should be collected and recorded on forms provided by AveXis within 24 hours of the site becoming aware.

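### The SAP looks for the sensory AESI in one MedDRA class only, under a narrower name, and does not reconcile the result with the AESIs that sites must report

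*SAP*

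**What the plan says.** Protocol 13.1.3 names four AESIs. The fourth is "Sensory abnormalities suggestive of ganglionopathy". The reporting duty covers "All AESIs (related and not related) that occur after signing of the informed consent through 30 days after the last study visit", and these, "irrespective of grade, should be collected and recorded on forms provided by AveXis within 24 hours of the site becoming aware". Protocol 12.1.2 puts sensory testing (proprioception, vibration, touch and pain) into the neurological examination at each visit and adds: "Any clinically significant abnormal finding should be recorded as an adverse event". Collection of ordinary adverse events in the eCRF ends earlier, at the last trial visit (Protocol 13.1.1).

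SAP 10.3.2.4 lists the AESIs, "which may be searched using Standardized MedDRA queries, will be summarized". Hepatotoxicity and cardiac events are found through named SMQs, and thrombocytopenia through two SMQs and one HLT. The fourth category reads "Ganglionitis, with potential cases identified by reviewing all TEAEs which code to the" Nervous System Disorders SOC. For every category, "the number and percentage of patients experiencing at least one TEAE in the search for the event of interest will be presented overall". SAP 10.3.1 closes the TEAE window at the last study visit.

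**The concern.** The protocol and the SAP define the same safety category differently. The protocol starts from what the site sees: any sensory abnormality that suggests ganglion disease. The SAP starts from how the event was coded, restricts the review to one organ class, and labels the category with a diagnosis. Nothing in the SAP brings the two together.

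The category has a reason to be read closely. Protocol 5.3 and 5.5 describe dorsal root ganglion inflammation, with neuronal necrosis or loss, in monkeys dosed intrathecally, and Protocol 5.5 commits to close monitoring of participants for clinical signs of it. The AESI table is where a reader will look for the outcome of that monitoring. In a trial of about 30 infants, a row of zero reads very differently from a row of one.

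**Working it through.** The documents give no power or precision figure for the AESI tables, so there is nothing to reproduce. The check compares the texts and then gives an illustration of size.

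**1. The two definitions side by side**

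| | Protocol 13.1.3 | SAP 10.3.2.4 |
|---|---|---|
| Name | Sensory abnormalities pointing to ganglionopathy | Ganglionitis |
| Found by | Site report, any grade, within 24 hours | Review of coded TEAEs |
| Scope | Not limited by coding | One SOC, Nervous System Disorders |
| End of window | 30 days after the last study visit | Last study visit (through the TEAE definition in SAP 10.3.1) |
| Link to the other source | – | None stated here or elsewhere in the SAP |

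**2. Can an event meet the protocol's definition and miss the SAP's?**

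- A sensory test is abnormal at a visit. Under Protocol 12.1.2 a clinically significant finding becomes an adverse event.
- The site judges it an AESI and reports it.
- The event is coded. SAP 10.3.2 says adverse event tables use the primary SOC.
- If that class is Nervous System Disorders, the event is reviewed. If it is any other class, it is outside the review and adds nothing to the row.

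The last step assumes that some sensory findings code elsewhere. MedDRA is not among the documents, so the frequency cannot be checked. The SAP does show that its authors expect terms for one clinical concept to spread across classes: a bilirubin-related listing in SAP 10.4.3 is built from a hepatic SMQ and then excludes terms in the Investigations SOC. Findings that start as examination results are natural candidates for the same spread.

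**3. The window**

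AESI reporting ends at the last visit plus 30 days; TEAEs end at the last visit. The difference is 30 days in which an AESI of any category is reportable but is not a TEAE under SAP 10.3.1. The SAP glossary (1.2) defines a TEAE without an end date, so the SAP is not uniform. The analysis section does give one, and Protocol 13.1.1 also stops ordinary adverse event collection at the last visit.

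**4. Size, as an illustration**

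Input: n = 30, the planned enrolment in Protocol 14.2, assumed to equal the number treated. Intervals are exact binomial (Clopper-Pearson), two-sided 95%.

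- One case counted: 1/30 = 3.3%. The lower limit is 1 − 0.975^(1/30) = 0.1%. The upper limit solves (1 − p)^30 + 30p(1 − p)^29 = 0.025, giving 17.2%.
- The same case missed: 0/30 = 0%. The upper limit is 1 − 0.025^(1/30) = 11.6%.

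Each missed patient lowers the reported incidence by 3.3 percentage points. The SAP plans no intervals for AESIs; these only show what one case is worth at this sample size.

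**The case against.** There is a good case on the other side, and much of it stands.

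- **The event is not lost from the report.** If it began by the last visit it appears in the TEAE tables by SOC and PT and the accompanying listing (SAP 10.3.2.2) and in the PT table (10.3.2.3). SAP 10.8 also lists post-infusion abnormal examination findings against baseline, with shift tables, and the neurologic system is one of those examined (4.6.3). A reader might infer that the case would vanish altogether. The documents do not support that. The loss is from the AESI table, although an event that begins after the last visit is also outside the TEAE tables.
- **No dedicated AESI form is documented.** Protocol 13.1.3 speaks only of sponsor-provided forms, in the words that 13.1.2 uses for SAEs, and the protocol's summary of changes calls them SAE forms. It is tempting to say that the SAP ignores an AESI dataset already in hand. The documents show neither such a dataset nor an AESI flag that could be analysed. They show a reporting duty that the SAP does not use; the SAP is silent on those reports and does not rule them out.
- **The argument does not reach all four categories equally.** Missed cases through coding are argued only for the sensory one. The other three rest on several standard queries, and liver and cardiac signals have their own analyses (SAP 10.4.3, 10.4.4, 10.6, 10.10). Only the window gap touches every category.
- **The search is permissive and broad.** The lead-in says that events may be searched, and a review of a whole organ class could over-count as easily as under-count. That is a fair point about events inside the class. It does not help an event outside it, and the counting rule still depends on the search.
- **The animal finding followed intrathecal dosing; this trial is intravenous.** Protocol 5.3 adds that the ganglion was not a target organ in previous studies, and Protocol 5.5 that a safety review to 31 December 2019 found no sensory events. That the AESI was created because of the monkey data is an inference. The protocol nevertheless made it an AESI and promised monitoring.

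**Conclusion.** The point holds for the sensory category. SAP 10.3.2.4 states a case-finding rule narrower than the protocol's definition in name, coding scope and time window, and nothing in the SAP reconciles it with the site reports. This is more than missing detail: the rule as written can give zero when a site has reported a case.

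The consequence is limited to the AESI table for events that begin by the last visit, and extends to the TEAE tables for later ones. At an assumed 30 treated infants, one case is the difference between 3.3% and 0%. The conclusion rests on the assumption that some sensory findings code outside Nervous System Disorders. The documents make this plausible but do not quantify it. They do not support the wider reading that all four AESI tables are unreliable.

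**What to change.** In SAP 10.3.2.4, for the fourth category:

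- use the protocol's category name;
- review all TEAEs, whatever their SOC;
- count an event if the site reported it as this AESI or the review found it;
- list events found by only one of the two sources;
- list AESIs with onset after the last visit.

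For hepatotoxicity, thrombocytopenia and cardiac events, keep the SMQ and HLT searches and add only a listing of site-reported AESIs that the search did not capture.

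The cost is a reconciliation against the sponsor's AESI and SAE reports and one more listing. The documents do not describe the format of those reports, so the effort cannot be stated exactly; at about 30 infants the review itself is small. AESI counts may rise slightly. No efficacy analysis changes and no extra patient assessment is needed.

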10.3.2.5. Related Adverse Events by Maximum Grade

Treatment-emergent adverse events and treatment-emergent adverse events with a "possibly related", "probably related", or "definitely related" of being related to AVXS-101 will be summarized by maximum grade of each preferred term. If a patient has an adverse event with

unknown grade, then the patient will be counted in the grade category of "unknown," even if the patient has another occurrence of the same event with a grade present.

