4.3. Safety Endpoints

Safety endpoint include physical examinations, pulmonary examinations, vital signs, capillary blood gas assessments, weight and length measurements, 12-lead ECGs, echocardiograms, 24-hour Holter monitors, swallowing tests, laboratory assessments, adverse event monitoring, and photographs of the infusion site. In general, safety assessments will be performed at the times scheduled in Table 1. All post-treatment visits are relative to the date on which gene replacement therapy is administered until the patient is 14 months of age, after which all visits will be relative to the patient’s date of birth.

The primary safety endpoint is the development of unacceptable toxicity, defined as the occurrence of any one Grade III or higher, unanticipated, treatment-related toxicity that presents with clinical symptoms and requires medical treatment

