10.3.2.2. Adverse Event by SOC and PT

The following summaries of adverse events will be generated:

- Serious adverse events for screen failure patients only;
- Treatment-emergent adverse events;
- Treatment-emergent adverse events occurring in two (2) or more patients;
- Treatment-emergent adverse events categorized as "related" to AVXS-101;
- Serious treatment-emergent adverse events;
- Serious treatment-emergent adverse events related to AVXS-101;
- Grade 4 treatment-emergent adverse events;
- Grade 3 or 4 (see definition below) treatment-emergent adverse events;
- Treatment-emergent adverse events leading to discontinuation of patient from study;
- Treatment-emergent adverse events leading to death;
- Treatment-emergent adverse events leading to concomitant medication use (events with other action taken of "concomitant medication prescribed").
- Treatment-emergent adverse events of special interest (see section 10.3.2.4);

For all adverse event summaries, the number of treatment-emergent adverse events, the number and percentage of patients experiencing treatment-emergent adverse events will be tabulated according to SOC and PT. Patients reporting more than one adverse event for a given PT will be counted only once for that term (most severe incident for the severity tables and most related incident for the relationship tables). Patients reporting more than one adverse event within a

SOC will be counted only once for that SOC. Patients reporting more than one adverse event will be counted only once in the overall total.

A listing by treatment group of treatment-emergent adverse events grouped by body system and preferred term with patient numbers will be created.

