10.3.2.3. Adverse Event by PT

The number of treatment-emergent adverse events and the number and percentage of patients experiencing treatment-emergent adverse events will be tabulated according to preferred term and sorted by overall frequency. Similar summaries will be provided for Grade 3 and 4 treatment-emergent adverse events and treatment-emergent adverse events with a "possibly related" to AVXS-101 categorization.

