10.3.2.6. Adverse Events by Maximum Severity Grade Level

Treatment-emergent adverse events will be summarized by maximum CTCAE grade level of each preferred term. Each preferred term will be assigned to a grade level based on severity and seriousness, adapted from CTCAE Version 4.03 for grading severity of adverse events.

All serious adverse events will be categorized according to Grade definition.

If a patient has a non-serious adverse event with unknown grade, then the patient will be counted in the severity grade level category of "unknown," even if the patient has another occurrence of the same event with a grade present.

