10.3.2.7. Adverse Events by Maximum Relationship

Treatment-emergent adverse events also will be summarized by maximum relationship of each preferred term to study drug (AVXS-101), as assessed by the investigator. If a patient has an adverse event with unknown relationship, then the patient will be counted in the relationship category of "unknown," even if the patient has another occurrence of the same event with a relationship present. The only exception is if the patient has another occurrence of the same adverse event with a relationship assessment of "possibly related" or higher. In this case, the patient will be counted under the "related" category.

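### The SAP's maximum-grade adverse event tables move a patient with a known Grade 3, 4 or 5 event to 'unknown' when another record of the same term is ungraded

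*SAP*

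**What the plan says.** Four places in SAP Section 10.3.2 bear on a patient who has more than one record of the same preferred term.

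- **10.3.2.2** sets a convention for all adverse event summaries: such a patient is "counted only once for that term (most severe incident for the severity tables and most related incident for the relationship tables"). It also lists a table of "Grade 3 or 4 (see definition below) treatment-emergent adverse events". 10.3.2.3 adds a version by preferred term: "Similar summaries will be provided for Grade 3 and 4 treatment-emergent adverse events".
- **10.3.2.5** tabulates all treatment-emergent events, and the related ones, by maximum grade per preferred term. A patient with an ungraded event goes to 'unknown' "even if the patient has another occurrence of the same event with a grade present". There is no exception.
- **10.3.2.6** tabulates treatment-emergent events by maximum CTCAE grade level. Its trigger is narrower: "If a patient has a non-serious adverse event with unknown grade, then the patient will be counted in the severity grade level category of" 'unknown', again regardless of any graded occurrence.
- **10.3.2.7** uses the same structure for relationship to study drug, but limits it: "The only exception is if the patient has another occurrence of the same adverse event with a relationship assessment of" possibly related or higher. That patient is counted as related.

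SAP 6.3 says that missing safety values, including adverse event data, are not imputed. No section says whether 10.3.2.5 and 10.3.2.6 override 10.3.2.2.

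**The concern.** A table headed maximum grade should not lose a patient whose maximum is already known to be severe. Under 10.3.2.5, one ungraded record removes the patient from the Grade 3, 4 or 5 row, even though the graded record alone puts the patient at Grade 3 or above. 10.3.2.6 does this when the ungraded record is non-serious.

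Two things follow. First, the same data can give a smaller Grade 3-4 count for a term in the maximum-grade tables than in the Grade 3-4 tables, with nothing in the SAP to explain the gap. Second, the shift always runs toward fewer patients shown at a known high grade. With about 30 treated infants, one patient is a visible fraction of any row.

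**Working it through.** The plan gives no figure to reproduce here. The check applies each counting rule to the same records and then scales the difference.

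**Inputs.** The counting rules of SAP 10.3.2.2, 10.3.2.5 and 10.3.2.6. Grades 1 to 5 from Protocol 13.1.1, Table 4. Death as a seriousness criterion from Protocol 13.1.2. A denominator of 30, the planned enrolment in Protocol 14.2.

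**Step 1: what is known about the true maximum.** Let g be the highest known grade and m the missing grade. The true maximum is max(g, m), which is never below g.

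| Known g | 10.3.2.5: m can be 1-5 | 10.3.2.6: ungraded record non-serious, so m can be 1-4 |
|---|---|---|
| 1 | 1 to 5 | 1 to 4 |
| 2 | 2 to 5 | 2 to 4 |
| 3 | 3, 4 or 5 | 3 or 4 |
| 4 | 4 or 5 | 4 (certain) |
| 5 | 5 (certain) | 5 (certain) |

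The right-hand column excludes m = 5 because a fatal event is serious under Protocol 13.1.2. For g = 3, 4 or 5, every possible value is Grade 3 or higher. For g = 1 or 2, the missing grade decides whether the patient reaches Grade 3. The SAP reports 'unknown' in every row.

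**Step 2: one patient, one term, under each rule.**

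| Records | 10.3.2.2 | 10.3.2.5 | 10.3.2.6 | In Grade 3-4 tables? |
|---|---|---|---|---|
| Grade 4 + ungraded non-serious | 4 | unknown | unknown | yes |
| Grade 3 serious + ungraded non-serious | 3 | unknown | unknown | yes |
| Grade 3 + ungraded serious | 3 | unknown | 3 | yes |
| Grade 1 + ungraded non-serious | 1 | unknown | unknown | no |
| Ungraded only | unknown | unknown | unknown | no |

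The 10.3.2.2 column uses known grades only. The 3 under 10.3.2.6 in the third row assumes that 10.3.2.2 applies when the 'unknown' rule is not triggered. In the first two rows both maximum-grade tables disagree with the Grade 3-4 tables. In the third row only the 10.3.2.5 table does.

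**Step 3: effect on a count.** Take four invented patients with one term, all ungraded records non-serious: A {4, missing}, B {3, 3}, C {3}, D {2, missing}.

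- SAP rule in 10.3.2.5 or 10.3.2.6: B and C at Grade 3-4, so 2/30 = 6.7%. A and D are unknown.
- Grade 3-4 table: A, B and C, so 3/30 = 10.0%.
- Rule proposed below: A, B and C at Grade 3-4, so 3/30 = 10.0%. D stays unknown.

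**Step 4: scale.** The change per term is k/30, where k is the number of patients with both a known Grade 3 or higher record and an ungraded record that triggers the rule. The documents give no missing-grade rate, so k is an assumption. For k = 0, 1, 2 and 3 the change is 0, 3.3, 6.7 and 10.0 percentage points.

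**The case against.** The case for leaving the text alone has real substance.

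- **The rule is express.** 10.3.2.5 and 10.3.2.6 address the ungraded case directly, and a programmer would follow them over the general convention. This stands: the SAP is not unworkable. It still does not state the precedence, and it still calls the result a maximum.
- **'Unknown' can be the honest answer.** A reader might infer that the highest known grade should always win. The documents do not support that. With a known Grade 1 or 2 the true maximum is undetermined, and reporting the known grade would treat the missing one as no worse.
- **The parallel with 10.3.2.7 is limited.** SAP 10.3.2.1 pools possibly, probably and definitely related into a single related category, so a known possibly related record is already at the top. Grade has five levels. The parallel shows that the authors protected a known worst category for relationship, but it does not by itself settle the rule for Grade 3 or 4. The argument there is that the patient is at least Grade 3 in any case.
- **Little is hidden.** Known Grade 3 and 4 events remain in the tables of 10.3.2.1 to 10.3.2.3, and fatal events in the table of events leading to death.
- **It may never arise.** Protocol 13.1.1 says "All AEs will be classified in accordance with the CTCAE version 4.03", and 13.3 asks for the intensity of each event.

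A reader might also infer that the primary safety endpoint is affected, since SAP 4.3 describes it as "defined as the occurrence of any one Grade III or higher, unanticipated, treatment-related toxicity". That does not follow. The endpoint also requires clinical symptoms and medical treatment. It cannot be derived from a table of maximum grade by preferred term under either counting rule.

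**Conclusion.** The point holds as a minor one, for patients with a known Grade 3 or higher record. For them, 'unknown' discards information that no value of the missing grade could overturn, and it lets two sets of tables disagree on the same data. It applies to 10.3.2.5 for any ungraded record and to 10.3.2.6 only for a non-serious one.

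The size is nil if every event is graded at lock. Otherwise it is 3.3 points per affected patient per term, assuming a safety population of the planned 30 and an assumed 0 to 3 affected patients. The text of the rule is certain; how often it would bite is not known. No hypothesis test, analysis population or stopping rule changes.

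**What to change.** In SAP 10.3.2.5 and 10.3.2.6:

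1. Add an exception: a patient with a known Grade 3 or higher record of the preferred term is counted at the highest known grade for that term.
2. Footnote the number of such patients who also have an ungraded record of the term.
3. State that this rule takes precedence over 10.3.2.2 for ungraded records.

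Leave 'unknown' in place for a known Grade 1 or 2 plus a triggering ungraded record, and for terms with no graded record.

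The cost is a short addition to two sections and one table footnote, with no new data and no imputation. The small downside is that a known Grade 3 in either table, or a known Grade 4 in the 10.3.2.5 table, is a lower bound on the true maximum. The footnote discloses this.
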